COMIRB Protocol

COLORADO MULTIPLE INSTITUTIONAL REVIEW BOARD
[name] [contact] [contact]

Protocol #:15-2388

Project Title: Discontinuation of Disease Modifying Therapies (DMTs) in Multiple Sclerosis (MS)

Principal Investigator: [name]

Version Date: 10Jan2020

I. Hypotheses and Specific Aims:

Main hypothesis is that relatively older MS patients with no recent signs of new inflammatory disease activity (no relapses for at least five years and no new brain MRI lesions for at least three years) while on an approved MS DMT may safely discontinue DMTs from a medical perspective, ie no greater risk of new relapses or brain MRI scan changes due to MS, compared to those staying on their DMT. Secondary hypotheses are that in individual MS patients who discontinue DMTs in this context, there will be no significant increased risk of disease progression as measured by the EDSS, and no worsening of patient quality of life as measured by a series of Patient Reported Outcomes (PROs), compared to those staying on their DMT.

Specific Aims:

In MS patients 55 years of age or older, who have no evidence of new relapses for at least five years or brain MRI lesions for at least three years while continuously taking DMTs, we will compare clinically significant and patient-relevant outcomes in those who discontinue vs continue DMTs to determine if:

1. Risk of new relapses or brain MRI lesions is no worse in those discontinuing
2. Risk of disability progression (EDSS) is no worse in those discontinuing
3. Quality of life and other patient-reported outcomes (PROs) are no worse in those discontinuing

II. Background, Preliminary Studies, and Significance:

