vii. **Treatment Decision Questions:** These question was also developed for exploratory purposes to gain insight on the MS DMT treatment decisions at the conclusion of the study and to better understand recruitment and retention, for patients who were randomized to either staying on or going off their DMT. The following question will be asked:

What do you plan to do for your MS medication after completing the study? Please circle one.

If you are in the continue group:

Stop my DMT Continue my current DMT Switch to a new DMT

If you are in the discontinue group:

Stay off of my DMT Re-start a prior DMT Re-start a new DMT

What is the main reason you participated in the DISCOMS study? Please circle one.

a) To possibly stop my MS medication, b) Increased access to doctor, nurse, and study team, c) Increased monitoring of my disease, ex. more frequent MRI, d) Possibility of saving money by going off my MS medication, e) Participation in clinical research to further medical knowledge of MS, f) Other: Please list other reason(s)

What is the main reason you stayed in the study? Please circle one.

a) To possibly stop my MS medication, b) Increased access to doctor, nurse, and study team, c) Increased monitoring of my disease, ex. more frequent MRI, d) Participation in clinical research to further medical knowledge of MS, e) Other: Please list other reason(s)

B. Description of Population to be Enrolled:

Inclusion criteria:

- RRMS, SPMS, or PPMS by McDonald 2010 criteria⁹. Patients will be defined by subtype based on 2013 updated phenotypic criteria¹⁶. Progression of MS will be defined by the local principal investigator either prospectively with an EDSS change of at least 1.0 points over the last two years, or retrospectively, with any significant change in motor function over at least one year, unrelated to relapse.
- 55 years of age or older at time of randomization;
- No evidence of recent new inflammatory disease activity (inactive by the Lublin criteria¹⁶) with no new relapse for at least five years and no new MRI lesion for at least three years
- Using any of the FDA-approved MS DMTs (to include interferon β-1a, interferon β-1b, glatiramer acetate, natalizumab, fingolimod, dimethyl fumarate, ocrelizumab, or teriflunomide; see exclusions below) continuously* for no less than 5 years.
- Taking most recent DMT continuously* for no less than two years.

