based on EDSS, or worsened patient quality of life, compared to continuers. This could be especially important for those discontinuing natalizumab, where there remains significant concern, and also disagreement, about the potential for not just recurrence of disease activity, but also significant rebound (ie, higher than prior baseline) of disease activity.^{63-65,70} As such, we will perform interim analyses at two pre-specified time points, when 25 (Tables 2, 4 below) and 65 (Tables 3, 5 below) patients in each group have completed their six-month evaluation or achieved the primary endpoint, ie if a participant has an acute relapse at any time, including before the T₁, 6 month safety check, or is noted to have a new or enlarging T2 brain MRI lesion, they will be considered to have achieved the primary endpoint. We would require the DSMB to consider discontinuing the study if either of the following occurred at either interim analysis time point:

- The difference in the proportion of events between the discontinue and continue groups was statistically significantly (alpha = 0.025) greater than 0.10. Presumably the discontinue group would be greater.
- If one group, presumably the discontinue group, had an event proportion statistically significantly (alpha = 0.025) greater than the expected number of cases defined by the continue group.

Primary endpoints will be defined as either:

1. "Relapse" will be defined as the appearance of new neurological symptoms or worsening of pre-existing neurological symptoms lasting at least 48 hours in a subject who had been neurologically stable or improving in the previous 30 days and accompanied by objective change in the neurological examination corresponding to that symptom (worsening of 0.5 point on the EDSS or worsening by 1.0 or more points on the pyramidal, cerebellar, brainstem or visual functional system score). Fatigue or subjective cognitive worsening, alone or in combination, will not be considered a "Protocol defined relapse."

Each Relapse event will be categorized on CRFs as one of the below:

• Protocol defined relapse

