It is possible a patient may have asymptomatic changes on a surveillance spine MRI scan, which is not part of the protocol or SOC. Most new spine lesions will have clinical symptoms and signs associated with them, however, limiting the significance of this issue.

F. Data Analysis Plan:

- a. Aim #1: Proposed Data Analysis: We will perform a non-inferiority test for the proportions of the discontinue and continue groups experiencing a binary, protocol-defined disease event within a year. A countable event will be a new protocol-defined relapse, and/or a new brain MRI lesion. We will test the null hypothesis of inferiority with the proportion of disease events for the discontinue group being 0.08 greater (i.e., 0.10 vs 0.02) than the proportion for the continue group under the alternative that the two rates are equal. Because of the expected small numbers of events, we expect to use likelihood based exact binomial methods to obtain a confidence interval for

comparing the proportions. If the upper bound of the 95% confidence interval for the difference between the groups is less than 0.08, then we can rule out discontinuation increasing the disease event proportion by 0.08 or greater. The anticipated small number of events, and the need to use exact methods, will constrain the models that can be used in analyses. Adjustment for center heterogeneity may be attempted with Cochran-Mantel-Haenszel test, but may be similarly limited by anticipated small number of events. We will also calculate estimates and confidence intervals, using exact methods as necessary, for the proportion of disease events in both the discontinue and continue groups. In the unlikely event the proportions are relatively large, we will also calculate estimates and confidence intervals for relative risks. Larger numbers of events would permit the fitting of more complex models

b. Aim #2: Proposed Data Analysis: We will calculate estimates and confidence intervals, using exact methods as necessary, for the proportion of disease events in both the discontinue and continue groups. Aim #2 assesses progression of disability as noted on the EDSS, and this will be defined as an increase of at least one point, confirmed at 6 months, for those with a baseline EDSS ≤ 5.5 , or a change of at least 0.5 for those with EDSS of 6.0 or greater at baseline. Outcomes assessed will include % of patients with confirmed progression in each group and mean change in EDSS in each group.

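### The Aim 2 definition of EDSS progression asks for 6-month confirmation only at baseline 5.5 or below, which conflicts with the confirmed-progression outcome it is meant to feed

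*Combined protocol and SAP*

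**What the plan says.** Section I (Specific Aims) sets the second aim: "Risk of disability progression (EDSS) is no worse in those discontinuing". Section III.F, Aim #2, then defines progression in one sentence with two limbs.

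- **Baseline EDSS 5.5 or below:** "an increase of at least one point, confirmed at 6 months, for those with a baseline EDSS" in that range.
- **Baseline EDSS 6.0 or above:** "or a change of at least 0.5 for those with EDSS of 6.0 or greater at baseline".

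The sentence that follows names what will be analysed: "Outcomes assessed will include % of patients with confirmed progression in each group and mean change in EDSS in each group". It makes no distinction by baseline EDSS.

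Table 1 in section III.C schedules the EDSS at baseline, at 6, 12, 18 and 24 months, and at unscheduled visits. No other section says how, or whether, progression is confirmed in the group at 6.0 or above.

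**The concern.** The confirmation requirement sits inside the first limb, ahead of that limb's own baseline condition, so grammatically it does not carry over to the second. The second limb also drops the word for an increase. The definition therefore does not deliver the confirmed outcome named in the next sentence for patients at 6.0 or above, and two programmers could produce two different event counts for a named specific aim.

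The group is unlikely to be empty. Section III.B admits secondary and primary progressive MS and lists no upper EDSS limit.

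The half-point step is also the size of movement that section III.D uses to establish a relapse: "worsening of 0.5 point on the EDSS or worsening by 1.0 or more points" on certain functional system scores. Without confirmation, a passing deterioration during a relapse could by itself enter Aim 2 as disability progression, which blurs Aim 2 with Aim 1. Confirmation six months later is what separates the two.

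**Working it through.** **1. The plan's own figure.** The only stated figure bearing on a binary EDSS outcome is the Aims 2-3 power statement in section III.F: at alpha 0.05, a difference in proportions of about 0.19 gives 80% power and 0.22 gives 90%. With 112 per arm, a two-sided test and proportions centred on 0.5 (no base rate is stated):

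- 0.405 vs 0.595 gives 81.6%
- 0.39 vs 0.61 gives 91.4%

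The figures reproduce, and this point does not dispute them.

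**2. Inputs for the illustration**

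- From the documents: four scheduled post-baseline EDSS visits, six months apart; 112 patients per arm.
- Assumed, because the documents do not give them: a truly stable patient, an error-free baseline, independent errors between visits, a chance q of a spurious half-point rise at each visit (3%, 5% or 10%), and 30% of patients starting at 6.0 or above.

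**3. Chance that a stable patient at 6.0 or above is counted**

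Unconfirmed rise at any of four visits: 1 − (1 − q)^4. Confirmed, meaning a rise at two consecutive visits among four: 3q² − 2q³.

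| q | Unconfirmed | Confirmed at next visit |
|---|---|---|
| 0.03 | 1 − 0.97^4 = 11.5% | 0.3% |
| 0.05 | 1 − 0.95^4 = 18.5% | 0.7% |
| 0.10 | 1 − 0.90^4 = 34.4% | 2.8% |

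(To more places, the first two unconfirmed values are 11.47% and 18.55%, hence about 11% and 19%.)

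**4. Patients per arm.** 0.30 × 112 = 33.6 at 6.0 or above.

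- Without confirmation: 33.6 × 0.1147 = 3.9; 33.6 × 0.1855 = 6.2; 33.6 × 0.3439 = 11.6. That is about 4 to 12 false progressors.
- With confirmation: 33.6 × 0.028 = 0.9 at most.

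These counts treat all 33.6 patients as truly stable, so they are upper figures for a given q.

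**5. Dilution of a true difference.** Suppose true progression is 15% vs 34% (assumed; difference 0.19, power 92% with 112 per arm). If a share s of patients is at 6.0 or above and a fraction f of the non-progressors among them is falsely counted, the observed difference is 0.19 × (1 − f × s). With s = 0.30:

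| q | f | Observed difference | Power |
|---|---|---|---|
| 0.03 | 0.115 | 0.184 | 88% |
| 0.05 | 0.185 | 0.179 | 85% |
| 0.10 | 0.344 | 0.170 | 78% |

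At q = 0.10, varying s from 0.20 to 0.40 moves the difference from 0.177 to 0.164 and power from 83% to 73%.

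**The case against.** The best defence is that the confirmation requirement is not missing, only unrepeated. The analysed outcome is stated as confirmed progression with no restriction by baseline EDSS, and a reader could take that to govern both limbs. This is a fair reading and may well be what was intended. It is the reason to say that the rule could be programmed without confirmation, not that it would be. It does not settle the matter: the sentence does not say when or how the second limb is confirmed, and the definition it relies on says something different.

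A reader might also infer that, because the second limb speaks of a change, improvement would be scored as progression. The documents do not support that. The clause completes a definition that opens "Aim #2 assesses progression of disability as noted on the EDSS", and the inclusion criteria use the same loose word, "prospectively with an EDSS change of at least 1.0 points over the last two years", where only worsening can be meant. No figure that counts falls in EDSS belongs in the assessment.

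Nor is it established that the gap favours a conclusion of no worse. Aim 2 states no non-inferiority margin. False events shrink the difference but also add variance and can widen the interval, so the net effect depends on how no worse is judged.

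Three limits on size also stand. At the lower assumed error rates the loss is modest. A mis-scored baseline would produce a lasting apparent rise that confirmation does not remove, so the confirmed figures are optimistic. And mean EDSS change, also an Aim 2 outcome, does not depend on this rule. Examining clinicians are blinded to assignment (section III.E), so the errors are plausibly similar in both arms; that fits dilution rather than a directional bias.

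**Conclusion.** The point holds as an inconsistency between a stated rule and the outcome it feeds. For baseline EDSS 6.0 or above, the definition lets a single unconfirmed half-point rise count, while the reported outcome is confirmed progression, and nothing elsewhere in the document reconciles them. The likely consequence is extra false events in both arms and a diluted difference.

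The size is illustrative only, since the error rates, the 30% share and the 15% vs 34% rates are all assumptions. Across those tried, about 11% to 34% of stable patients in the group would be counted without confirmation, against 0.3% to 2.8% with it. The contrast between the two is large throughout; the effect on the overall Aim 2 comparison ranges from slight to moderate. This is a secondary endpoint and the primary analysis is untouched, but the correction should be made before Aim 2 is programmed.

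**What to change.** Reword the second limb to match the first, for example: *or an increase of at least 0.5 point, confirmed at 6 months, where baseline EDSS is 6.0 or greater*. Both limbs then agree with the confirmed-progression outcome.

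State also how a first rise at the last scheduled visit is classified. No later scheduled visit can confirm it (T4, or T3 for participants who have no T4 visit), so under a confirmation rule it would not count, in either limb. Section III.C allows an early, out-of-window T4 for late enrolees: a T3 on 30 June 2021 would be followed by a T4 before 1 September 2021, about two months later. The text should therefore say whether such a visit can serve as confirmation.

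The cost is one phrase plus a short handling rule. EDSS is already scored every six months, so no new data or visits are needed. The price is that a few genuine late progressions go uncounted.

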Comorbidities	X	X	X	X	X	X	
Neuro-QoL Short Form	X	-	-	****	X	X	
PDSS	X	X	X	X	X	X	
SymptoMScreen	X	X	X	X	X	X	
MSIS-29	X	X	X	X	X	X	
SDMT	X	X	X	X	X	X	
Treatment Satisfaction Question	X	X	X	X	X	X	
Relapse Assessment	X	X	X	X	X	X	
EDSS (by unbiased Rater)	X	X	X	X	X	X	
Treatment Decision Questions	-	-	-	****	X	X	
MRI**	X	X	X	****	X	-	

*Unscheduled visits may occur for patients during the study. If an MRI is requested by the PI in relation to an unscheduled visit, that MRI would be paid through standard of care.

**T₀, T₂, and T₄ MRIs paid as part of standard of care (SOC). T₁ MRI paid as research only and must be performed at the study site. T₀ Brain MRI to be performed within 6 months preceding study entry, and will be reviewed and confirmed as fulfilling entry criteria. If T₀ MRI results for a potential subject from within the last 6 months are not available, the patient should be scheduled for a Standard of Care MRI and these results should be reviewed for inclusion/exclusion criteria prior to enrollment into the study and completion of Baseline visit.

***Participants enrolled after July 31, 2019 may not complete T₄, but will be followed until September 1, 2021. If T₃ is on or before June 30, 2021, participant should come in for an out of window T₄ visit before Sept. 1, 2021.

****If T₃ falls after June 30, 2021, participants will not come in for a T₄ visit, but will complete a NeuroQoL and Treatment Decision Question during T₃, and will have an out of window Month 24 MRI.

After thorough discussion of the trial and signing an informed consent, participants will be seen at five specified time points: T₀, screen/baseline; T₁ at 6 months; T₂ at 12 months; T₃ at 18 months; and T₄ at 24 months. Patients will be screened, have a baseline brain MRI reviewed, undergo a relapse assessment and EDSS exam, complete all PROs, and be randomized at T₀. They will be examined every 6 months at times T₀, T₁, T₂, T₃, and T₄ and undergo MRI scans of the brain at times T₀, T₁, T₂, and T₄. If T₃ occurs after June 30, 2021, participants will not be seen for a T₄ visit and they will complete the NeuroQoL and Treatment Decision Question during T₃. If the T₃ visit occurs on or before June 30, 2021, the patient will be brought back in for a T₄ visit prior to September 1, 2021. Patients who have finished the study prior to protocol v. 10Jan2020 approval will be contacted via phone to obtain verbal consent, and will then be asked the Treatment Decision Question.

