c. Aim #3: Proposed Data Analysis: Descriptive statistics on patient demographics, PDSS, MSIS, performance and NeuroQOL short form scales, and all other PROs will be prepared for treatment group by occurrence of disease event, and qualitatively compared. Pre-Post change will be compared between treatment groups. Change scores will be used for continuous and metric outcomes, and the treatment groups will be compared with two sample T-tests, or Wilcoxon tests if necessary. Binary outcomes, such as dichotomized changes in EDSS and other scales, will be tested with chi-square and proportion tests, or exact analogs if necessary. MSIS will be divided into patients with greater or less than a change of 7.5 (considered a significant change). Correlations between continuous scales will be examined, and compared between treatment groups. Events will also be compared to non-events, and combinations of (event outcome) will be tested for differences, using similar methods, in the unlikely situation there are enough events to permit meaningful statistical analysis (≥ 10 samples for an analysis group). Multiple groups can be tested with ANOVA methods for continuous outcomes, and with chi-square tests and logistic regression for binary outcomes.

Sample Size Estimation: Our null hypothesis for AIM #1, inferiority of the discontinue group, is a disease event proportion of 0.02 for the continue group, and 0.10 for the discontinue group. Our alternate hypothesis for the power calculation, non-inferiority of the discontinue group, is a disease event rate of 0.02 for both the continue and discontinue groups. Our study population consists of stable patients, so we expect the disease event rate to be very small for the continue group, and possibly the discontinue group as well. For a target alpha level of 0.025, a sample size of 112 per treatment group (225 total), would achieve 95% power for the non-inferiority test. For a single treatment group with 112 samples, if the true proportion is 0.02, then the upper bound of an exact confidence intervals can be expected to be less than 0.11 more than 95% of the time. Anticipating a dropout rate of approximately 9-15%, we plan to attempt to recruit 132 patients per treatment group (265 total).

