For secondary outcomes AIMS 2-3, a two sample t-test comparing change scores between treatment groups with an alpha level of 0.05 and an effect size equal to 38% of the standard deviation would achieve 80% power, and an effect size of 44% of the standard deviation would achieve 90% power. A two sample proportion difference test between treatment groups with an alpha level of 0.05 and an effect of approximately 0.19 would be able to achieve 80% power, and an effect of 0.22 would achieve 90% power. A relative risk test with an alpha level of 0.05, a control proportion of 0.3

or 0.5, and a ratio of 1.61 or 1.37 respectively would achieve 80% power, and a ratio of 1.71 or 1.42 respectively would achieve 90% power. A Pearson correlation of 0.27, within a group of 112 samples, between two normally distributed variables, would be detectable with 80% power for an alpha level of 0.05, and a Pearson correlation of 0.30 would be detectable with 90% power.

Table 2: Safety Comparisons of the two groups at 25 patients in each group

Sample per Group = 25		
Group	# of Events	Percent
Continue	0	0.00
Discontinue	7	28.00
Proportion		
Difference Estimate	95% Confidence Interval	
0.2800	0.1067	0.4939

Sample per Group = 25		
Group	# of Events	Percent
Continue	1	4.00
Discontinue	10	40.00
Proportion		
Difference Estimate	95% Confidence Interval	
0.3600	0.1311	0.5765

Table 3: Safety Comparisons of the two groups at 65 patients in each group

Sample per Group = 65		
Group	# of Events	Percent
Continue	1	1.54
Discontinue	15	23.08
Proportion		
Difference Estimate	95% Confidence Interval	
0.2154	0.1083	0.3407

Table 4: pValues in Dark Grey
denote statistically significant events
in discontinuers (vertical axis) vs
continuers (horizontal) at interim
analysis of 25 patients in each group.

Sample per Group = 25							
Null Hypothesis for p (Expected # of Events)							
# of Events	0.02 (0.5)	0.04 (1)	0.08 (2)	0.10 (2.5)	0.12 (3)	0.16 (4)	0.20 (5)
1	0.3965	0.6399	0.8756	0.9282	0.9598	0.9872	0.9962
2	0.0886	0.2642	0.6053	0.7288	0.8195	0.9263	0.9726
3	0.0132	0.0765	0.3232	0.4629	0.5912	0.7870	0.9018
4	0.0014	0.0165	0.1351	0.2364	0.3525	0.5837	0.7660
5	0.0001	0.0028	0.0451	0.0980	0.1734	0.3707	0.5793
6	0.0000	0.0004	0.0123	0.0334	0.0709	0.2002	0.3833
7	0.0000	0.0000	0.0028	0.0095	0.0243	0.0920	0.2200
8	0.0000	0.0000	0.0005	0.0023	0.0070	0.0361	0.1091
9	0.0000	0.0000	0.0001	0.0005	0.0017	0.0243	0.0468
10	0.0000	0.0000	0.0000	0.0001	0.0004	0.0035	0.0173

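### Aim 3 tests one undefined pre-post change for scales measured at four post-baseline visits, so interim scores go unused and patients without T4 may drop out of the comparison

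*Combined protocol and SAP*

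**What the plan says.** Section III.C sets five visits: "They will be examined every 6 months at times T₀, T₁, T₂, T₃, and T₄". Table 1 marks PDDS (printed there as PDSS), SymptoMScreen, MSIS-29, SDMT and the treatment satisfaction question at all five. Neuro-QoL is marked at baseline and T4, with T3 standing in when there will be no T4 visit.

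Section III.F, Aim #3, gives the between-arm comparison: "Pre-Post change will be compared between treatment groups". For continuous scales, "the treatment groups will be compared with two sample T-tests, or Wilcoxon tests if necessary". Dichotomised changes, including the 7.5-point split of the MSIS, go to chi-square, proportion or exact tests. ANOVA and logistic regression are mentioned for multiple groups. The section does not say which visit is post, whether T3 may replace T4 for the repeated scales, or how missing scores are handled.

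The power statement for Aims 2 and 3 uses the same single-change test: "an effect size equal to 38% of the standard deviation would achieve 80% power". For 90% power it gives 0.44 SD.

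The footnotes to Table 1 say that participants whose T3 falls after 30 June 2021 have no T4 visit, and that other late enrolees have T4 out of window, before 1 September 2021. Section III.E warns that patients who do not get the assignment they wanted may be more likely to leave.

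**The concern.** Aim 3 asks whether patients are no worse off without a DMT. Two things decide how well the comparison answers that: who is in it, and how wide its interval is.

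A two-sample test on one change uses only patients who have both values. Here the final value can be missing for two foreseeable reasons. Some late enrolees have no T4 visit by design. Others may drop out, and the protocol itself links dropout to the assigned arm. Most of these patients will have some interim scores, but Aim 3 gives those scores no role in the comparison. Patients know their assignment, so a comparison of completers is exposed to selective loss.

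The open definition of post adds a second problem. T4, T3 in place of T4, or the last attended visit would each give a different analysis set and a different estimand, and the choice could be made after the data are seen.

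**Working it through.** **Inputs from the protocol.** 112 completers per group; 132 recruited per group; dropout 9-15%; alpha 0.05 (two-sided assumed, as the plan does not say); detectable effects of 0.38 and 0.44 SD of the change score; four post-baseline visits.

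**Input assumed.** The correlation between visits, which the documents do not give. I take 0.5 to 0.9, either equal for all pairs of visits (compound symmetry) or as the adjacent-visit value decaying with time (AR(1)).

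**1. The plan's own figures.** Power = Φ(d√(n/2) − 1.96), with √(112/2) = 7.483.
- d = 0.38: Φ(2.844 − 1.96) = 81.2% (noncentral t 80.8%); stated 80%.
- d = 0.44: Φ(3.293 − 1.96) = 90.9% (noncentral t 90.6%); stated 90%.

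Both reproduce at 112 per group. Recruitment also reproduces: 112/0.85 = 132. The power statement is therefore built on completers, and 132 − 112 = 20 per arm lie outside it.

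**2. If still more patients lack the post value.** The number without T4 is not given, so this is a range. With 5, 10, 15 or 20% of the 112 missing (106, 101, 95 or 90 left per arm), power at 0.38 SD is 79, 77, 75 or 72%.

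**3. Gain from including baseline, same 112 completers.** Let r be the correlation between baseline and T4. A change score has variance 2(1 − r) per patient, and a baseline-adjusted score has 1 − r². The standard-error ratio is √[(1 + r)/2].
- Compound symmetry: r = 0.5 gives 0.866; r = 0.9 gives 0.975.
- AR(1): adjacent correlation 0.5 means r = 0.5⁴ = 0.0625, ratio 0.729; adjacent correlation 0.9 means r = 0.656, ratio 0.910.

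**4. Gain from adding T1-T3 and the partial completers.** Generalised least squares with a common baseline mean, visit effects and arm-by-visit effects; 132 per arm, 112 with T4, and the other 20 spread evenly over last visits T0 to T3 (five each).

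| Structure, correlation | T4 SE: adjusted completers ÷ planned | T4 SE: full model ÷ planned | Full model ÷ adjusted completers |
|---|---|---|---|
| Compound symmetry, 0.5 | 0.866 | 0.858 | 0.990 |
| Compound symmetry, 0.9 | 0.975 | 0.958 | 0.982 |
| AR(1), 0.5 | 0.729 | 0.724 | 0.993 |
| AR(1), 0.9 | 0.910 | 0.887 | 0.974 |

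Against the planned test, the T4 standard error falls by 4-14% or 11-28%. The last column shows that the interim visits and partial completers account for about 1-3% of further reduction. If all 20 per arm miss only T4, that becomes about 2-5%. At a true T4 effect of 0.38 SD, power rises from 81% to 84-91% (compound symmetry) or 89-98% (AR(1)).

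**5. Averaging T1-T4 instead.** Under compound symmetry the mean of four changes has variance (1 + 3r)/4 + 1 − 2r = 5(1 − r)/4. Divided by 2(1 − r), this is 0.625 for any r, so the standard error is 21% smaller (√0.625 = 0.79). That estimates a 6-24-month average. If the arm difference grows linearly to T4, its average is (0.25 + 0.5 + 0.75 + 1)/4 = 0.625 of the T4 effect. With 112 per arm and a T4 effect of 0.38 SD, power for the average is then Φ(0.38 × 0.625/0.79 × 7.483 − 1.96) = 61%, or 71% under AR(1) at 0.8, against 81% for the planned test.

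**The case against.** The planned test is valid for what it is, and its stated power is correct, so there is no arithmetic error. Post is undefined, and no rule excludes patients without T4. Moving Neuro-QoL to T3 when T4 will not occur may hint that a last attended visit would serve. Patients who reach the primary endpoint stay on all visits. Section III.A also gives PDDS a use at every time point, to characterise and control for disability, and Aim 3 promises descriptive statistics on the PROs. All of this stands: the exclusion of patients without T4 is an inference from the completer-based sizing, and the interim scores are absent from the stated between-arm comparison but not from every use.

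A reader might go further and infer that the plan throws away the equivalent of 60% more patients (1/0.625 = 1.6), or that the detectable effect could fall from 0.38 to 0.30 SD. The documents do not support that. Those figures belong to the T1-T4 average, a different question from the 24-month difference, and they help only if the effect is the same at every visit. Section II names acceleration of progression among patients' main fears about stopping. An effect of that kind would build up over time, and averaging would dilute it (step 5).

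A longitudinal model also leaves the protocol's own caveat in place: unblinded patients may report differently by arm.

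**Conclusion.** The point holds as a weakness of method and of missing-data handling. Aim 3 names one change score, leaves its end visit undefined, and gives no between-arm use for three of four scheduled assessments on five instruments. Neuro-QoL lies outside the point.

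The T4 standard error could be about 4-14% (compound symmetry) or 11-28% (AR(1)) lower, mostly from including baseline; the repeated visits add about 1-3%. This rests on assumed correlations of 0.5-0.9, on 20 of 132 per arm lacking T4 with losses spread evenly over visits, and on post meaning T4 without imputation. The stronger reason to act is retention: leavers and patients without T4 by design contribute their earlier scores under missing-at-random, a weaker assumption than a completer comparison needs. The number of such patients is not in the documents, so the size of that benefit cannot be fixed. This is a cheap improvement that should be made.

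**What to change.** - Define post as T4 (24 months), and state how T3 and out-of-window T4 scores are treated for the repeated scales.
- For MSIS-29, SymptoMScreen and SDMT, make the main analysis a repeated-measures model of all T1-T4 scores with baseline, visit, arm, arm-by-visit and unstructured covariance. Baseline may be a covariate, or a response with a common mean across arms. It must be in the model: under compound symmetry at correlation 0.8, the plain mean of four post-baseline scores has variance 0.85 against 0.40 for the planned change, 2.1 times as large.
- Lead with the T4 arm difference and its 95% interval. Report the T1-T4 average as secondary.
- Use an ordinal analogue for PDDS and the five-level satisfaction item.
- Keep the two-sample change-score test as a check. Leave Neuro-QoL on its single post-baseline assessment.

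The cost is analysis-plan wording and programming, with no new data. The downside is reliance on missing-at-random. The model does not remove bias from unblinded reporting or from informative dropout, and the write-up should say so.
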